**Please go to the next page**

		Very Dissatisfied	Dissatisfied	Somewhat Dissatisfied	Neither Satisfied nor Dissatisfied	Somewhat Satisfied	Satisfied	Very Satisfied
9.	With the ease of cleaning your inhaler?							
10.	With using the inhaler?							
11.	With the speed at which medicine comes out of the inhaler?							
12.	With the ease of holding the inhaler during use?							
13.	With the overall convenience of carrying the inhaler with you?							
14.	Overall, how satisfied are you with your inhaler?							

**Please go to the next page**

**PART 2: RATING OF WILLINGNESS TO CONTINUE WITH INHALER**

15. How would you feel about continuing to use the inhaler?

Please indicate your willingness to continue using the inhaler that you used during the study by providing a value between 0 and 100.

0 indicates that you would not be willing to continue using this inhaler and 100 indicates that you would definitely be willing to continue.

Please write in a number in the box that is between 0 and 100.

**Inhaler**

**The box should contain a number between 0 and 100.**

1. LIST OF ABBREVIATIONS AND DEFINITION OF TERMS

ADR	Adverse Drug Reaction
AE	Adverse Event
BMI	Body Mass Index
CAT	COPD Assessment Test
CI	Confidence Interval
COPD	Chronic Obstructive Pulmonary Disease
CSP	Clinical Study Protocol
CSR	Clinical Study Report
DBL	Database Lock
DBP	Diastolic Blood Pressure
DPI	Dry Powder Inhaler
DRM	Data Review Meeting
eCRF	electronic-Case Report Form
ECSC	European Coal and Steel Community
FAS	Full Analysis Set
FEV	Forced Expiratory Volume
FVC	Forced Vital Capacity
GOLD	Global Initiative for Chronic Obstructive Lung Disease
ICF	Informed Consent Form
ICS	Inhaled Corticosteroids
LABA	Long-Acting Beta ₂ -Agonists
LAMA	Long-Acting Muscarinic Antagonists
MDI	Metered Dose Inhaler
MedDRA	Medical Dictionary for Regulatory Activities
Non-SAE	Non-Serious Adverse Event
PASAPQ	Patient Satisfaction and Preference Questionnaire
PT	Preferred Term
Q1	First Quartile
Q3	Third Quartile
RWS	Real-World Solutions
SAE	Serious Adverse Event
SAP	Statistical Analysis Plan

Document: \\ .net\Enterprise\Sites\USCBG\Depts\BioStat\Boehringer\Documentation\SAP\Final

Author: Version Number: 1.0
Version Date: 100CT2019

Template No.: RWI_TP_BIOS0013 Revision 1

Reference: RWI_WI_BIOS0015

Effective Date: 15Jun2018

SBP	Systolic Blood Pressure
SD	Standard Deviation
SMI	Soft Mist™ Inhaler
SOC	System Organ Class
TLFs	Tables, Listings and Figures
WHO-DD	World Health Organization Drug Dictionary

Document:	\\ .net\Enterprise\Sites\USCBG\Depts\BioStat\Boehringer\Documentation\SAP\Final
Author:	Version Number: 1.0
	Version Date: 100CT2019

Template No.: RWI_TP_BIOS0013 Revision 1

Reference: RWI_WI_BIOS0015

Effective Date: 15Jun2018

2. INTRODUCTION

The purpose of this Statistical Analysis Plan (SAP) is to provide a comprehensive and detailed description of the strategy and statistical methodology to be employed in the analysis of this non-interventional study assessing patient satisfaction with and preference for re-usable Respimat® Soft Mist™ Inhaler (SMI) in patients with chronic obstructive pulmonary disease (COPD).

This version of the SAP is created based on the current study protocol version 1.0, dated 11 June 2019 and electronic-Case Report Forms (eCRFs) version 2.0, dated 23 July 2019. Results of the analyses described in this SAP will be included in the Clinical Study Report (CSR). Additionally, the planned analyses identified in this SAP may be included in regulatory submissions and/or manuscripts. Any unplanned analyses performed to provide results for inclusion in the CSR but not identified in this prospective SAP will be clearly identified in the CSR.

The study aims to assess patient satisfaction with the inhaler attributes of the re-usable Respimat® SMI (Spiriva® 2.5 µg inhalation solution, Striverdi® 2.5 µg inhalation solution or Spiolto® 2.5 µg / 2.5 µg inhalation solution) in adult patients (aged 40 years and above) with COPD, including patients who are Respimat® SMI-experienced and Respimat® SMI-naïve. In addition, patient preference for the re-usable Respimat® SMI compared to the disposable Respimat® SMI in Respimat® SMI-experienced patients switching from a disposable to a re-usable Respimat® SMI product at study entry will also be analysed.

Document: \\ .net\Enterprise\Sites\USCBG\Depts\BioStat\Boehringer\Documentation\SAP\Final
Author: Version Number: 1.0
Version Date: 100CT2019

Template No.: RWI_TP_BIOS0013 Revision 1

Reference: RWI_WI BIOS0015

Effective Date: 15Jun2018

3. STUDY OBJECTIVES

3.1 Primary Objectives

The primary objective of the study is to assess patient satisfaction with the re-usable Respimat® SMI measured by the total score of a validated Patient Satisfaction and Preference Questionnaire (PASAPQ) at study end.

3.2 Secondary Objectives

The secondary objectives of the study are as follows:

For all *Respimat® SMI patients*:

- 1) To examine the individual domains of the PASAPQ: total performance score, total convenience score, the overall satisfaction question and the question on willingness to continue with inhaler at study end.
- 2) To examine the ease of handling of the re-usable Respimat® SMI at study end.

Additionally, for *Respimat® SMI-experienced patients switching from a disposable to a re-usable Respimat® SMI at study entry*:

- 3) To compare the difference in the mean total PASAPQ score between study entry and study end.
- 4) To examine patient preference for the re-usable Respimat® SMI, through a single question asking patients their preference for the re-usable compared to the disposable Respimat® SMI at study end.

Document: \\ .net\Enterprise\Sites\USCBG\Depts\BioStat\Boehringer\Documentation\SAP\Final

Author: Version Number: 1.0
Version Date: 100CT2019

Template No.: RWI_TP_BIOS0013 Revision 1

Reference: RWI_WI_BIOS0015

Effective Date: 15Jun2018

4. STUDY DESIGN

4.1 General Description

This is a multicentre, open-label, prospective, real-world non-interventional study of patients with COPD, prescribed with re-usable Respimat® SMI. Patient enrolment will commence in September 2019 and is expected to end in December 2019. The last patient last assessment is expected in February 2020 (see Section 6 of the Clinical Study Protocol [CSP] for details of study milestones).

For this study, two patient cohorts will be defined according to the prescription of a Respimat® SMI product:

- 1) Respimat® SMI-experienced, defined as patients who have been on maintenance treatment with a Respimat® SMI product (Spiriva®, Striverdi® or Spiolto®) and receive a refill prescription at study entry. This patient cohort will further be divided into two subgroups:
 - 1a) Patients on maintenance treatment with a re-usable Respimat® SMI at study entry.
 - 1b) Patients on maintenance treatment with a disposable Respimat® SMI and switching to a re-usable Respimat® SMI at study entry.
- 2) Respimat® SMI-naïve, defined as patients who have not previously used a Respimat® SMI product and receive their first prescription at study entry.

The prescription at study entry for both patient cohorts should be for a re-usable Respimat® SMI product.

Document:	\	.net\Enterprise\Sites\USCBG\Depts\BioStat\Boehringer\Documentation\SAP\Final
Author:		Version Number: 1.0

Template No.: RWI_TP_BIOS0013 Revision 1

Reference: RWI_WI_BIOS0015

Effective Date: 15Jun2018

The study population will be identified by the participating physicians involved in the diagnosis, treatment and management of COPD patients (general practitioners and/or specialist physicians including pneumologists). Eligible patients must be prescribed and use a re-usable Respimat® SMI product (as per the routine clinical practice of the participant sites) after being prescribed a Respimat® SMI product for the first time in the course of standard clinical practice (Respimat® SMI-naïve patients) or after having switched from a disposable Respimat® SMI (Respimat® SMI-experienced patients).

[figure not shown]
Eligible patients will be asked to provide written informed consent prior to the inclusion in the study. Each patient will be followed prospectively from the time of enrolment until the earliest of: death, loss to follow-up or end of the study period (i.e. approximately 4-6 weeks after the enrolment visit). Patients who are alive and not lost to follow-up, will have a follow-up assessment at the end of the study period ([Figure 1](#)). An additional 2-week follow-up window has been included to account for scheduling of clinic visits and/or provision of time for the patient to complete the PASAPQ and the questions on the ease of handling of the re-usable Respimat® SMI.

Document: \\ .net\Enterprise\Sites\USCBG\Depts\BioStat\Boehringer\Documentation\SAP\Final
Author: Version Number: 1.0
Version Date: 100CT2019

Template No.: RWI_TP BIOS0013 Revision 1

Reference: RWI WI BIOS0015

Effective Date: 15-Jun-2018

**Figure 1 Study design**

4.2 Schedule of Events

Patients will have two assessments for data collection: one at study enrolment (baseline visit) corresponding to their routine clinic visits for treatment of COPD, and one at the end of the study period (follow-up assessment), which will occur approximately 4-6 weeks after the baseline visit. The follow-up assessment can be completed during a routine clinic visit or remotely (by telephone) if the patient does not visit the site (clinic) within 4-6 weeks of the baseline visit.

No additional clinic visits or assessments are mandated or recommended for this study.

All patients will have the PASAPQ administered at study end (follow-up assessment). For the Respimat® SMI-experienced patients switching from a disposable to a re-usable Respimat® SMI product at study entry, the PASAPQ will be administered twice: (1) at study enrolment (baseline visit); and (2) at study end (follow-up assessment). Patients unable to complete the PASAPQ

Document:	\	.net\Enterprise\Sites\USCBG\Depts\BioStat\Boehringer\Documentation\SAP\Final	
Author:		Version Number:	1.0
		Version Date:	100CT2019

Template No.: RWI_TP_BIOS0013 Revision 1

Reference: RWI_WI_BIOS0015

Effective Date: 15Jun2018

electronically may be provided with a paper version of the PASAPQ at study enrolment (baseline visit), if applicable. It can also be mailed (with a pre-paid return envelope) to patients to be completed up to 2 weeks after study completion (follow-up assessment).

The pack size for the re-usable Respimat® SMI will cover 30 days (1 month), or 90 days (3 months), depending on the country. It is therefore anticipated that patients prescribed larger pack sizes may not return to the clinic at the time of follow-up assessment. Therefore, the PASAPQ, as well as the questions on the ease of handling of the re-usable Respimat® SMI and patient preference, will be administered either electronically or mailed to patients (depending on patient preference) to be completed offsite (remotely).

The study timepoints throughout the study are outlined in the visit flow chart below ([Table 1](#)).

Table 1 Visit flow chart and data variables to be collected

	Study entry (Baseline)	Follow-up assessment (4-6 weeks after baseline)
Informed Consent	X	
Inclusion / Exclusion Criteria	X	
Patient demographics (e.g. age, gender, height, weight, highest level of educational attainment)	X	
Duration of COPD	X	
CAT or mMRC score (if available)	X	
Pulmonary function (based on most recent spirometry test in the 12 months prior to study entry ¹) (if available)	X	
Disease severity based on 2019 GOLD grade and group ²	X	
Respimat® SMI product prescribed (Spiriva®, Striverdi® or Spiolto®)	X	
Duration of treatment with disposable Respimat® SMI ³	X	
Last day of use of disposable Respimat® SMI ³	X	
Date of first prescription of re-usable Respimat® SMI	X	
Number of COPD exacerbations (in the 12 months prior to study entry) and during the study period	X	X

Document: \\ .net\Enterprise\Sites\USCBG\Depts\BioStat\Boehringer\Documentation\SAP\Final

Author: Version Number: 1.0

Version Date: 100CT2019

Template No.: RWI_TP_BIOS0013 Revision 1

Reference: RWI_WI_BIOS0015

Effective Date: 15Jun2018

	Study entry (Baseline)	Follow-up assessment (4-6 weeks after baseline)
COPD-related concomitant medications (in the 6 months prior to study entry and during the study period ⁴)	X	X
Comorbidities	X	X
Smoking status / history	X	X
PASAPQ completed by the patient ⁵	X	X
Respimat® SMI type used during study period (disposable or re-usable)		X
Questions on the ease of handling of re-usable Respimat® SMI		X
Question on Respimat® SMI preference (disposable vs re-usable) ⁵		X
Safety: Serious and non-serious ADRs, AEs with a fatal outcome, and other reportable safety events		X
Details of discontinuation of the re-usable Respimat® SMI during the study period ⁴ (if applicable)		X

¹ If more than one measurement is available in the 12-month period prior to study entry, the measurement closest to the study entry will be included.

² GOLD patient group (A, B, C or D) will be appraised based on available exacerbation history, assessment of symptoms based on CAT, and GOLD grade (1-4) spirometry classification of airflow limitation based on post-bronchodilator spirometry results, if available (GOLD 2019 [1]).

³ This will be assessed in Respimat® SMI-experienced patients only.

⁴ The study period starts with the baseline visit and ends with the follow-up assessment, which is approximately 4-6 weeks.

⁵ PASAPQ at study enrolment (baseline visit) and the question on Respimat® SMI preference (disposable vs re-usable) will be administered only to the Respimat® SMI-experienced patients switching from disposable to re-usable Respimat® SMI at the time of study entry.

ADR: Adverse Drug Reaction; AE: Adverse Event; CAT: COPD Assessment Test; COPD: Chronic Obstructive Lung Disease; GOLD: Global Initiative for Chronic Obstructive Lung Disease; mMRC: modified Medical Research Council PASAPQ: Patient Satisfaction and Preference Questionnaire; SMI: Soft Mist™ Inhaler.

4.3 Changes to Analysis from Protocol

This section summarises changes in analysis or definitions from those planned in the protocol.

The protocol history table below ([Table 2](#)) gives the timing, rationale, and key details of major changes to the statistical methods described in the protocol statistical section.

Document:	\	.net\Enterprise\Sites\USCBG\Depts\BioStat\Boehringer\Documentation\SAP\Final	
Author:		Version Number:	1.0
		Version Date:	100CT2019

Template No.: RWI_TP_BIOS0013 Revision 1

Reference: RWI_WI_BIOS0015

Effective Date: 15Jun2018

Table 2 Protocol amendment statistical changes

Amendment Number	Date Approved	Rationale	Significant Changes from Previous Authorised Version
No Changes			

5. PLANNED ANALYSES

The following analysis will be performed for this study:

- Final Analysis.

5.1 Interim Analysis

No interim analysis is currently planned for the study.

5.2 Final Analysis

The final analysis outlined in this SAP will be performed by Real-World Solutions (RWS) Biostatistics following the Database Lock (DBL). A dry-run analysis and a Data Review Meeting (DRM) will be held prior to partial DBL. The main purpose of the dry-run is the initial production of the dry-run Tables, Listings and Figures (TLFs) shells contained in the finalized SAP using whatever data presented in the current database (data that has not been cleaned). In addition, the database cannot be locked until this SAP has been approved.

6. SAMPLE SIZE CALCULATION

The primary objective of this study is to assess patient satisfaction with the re-usable Respimat® SMI, measured by the total mean score of PASAPQ. Assuming a population standard deviation

Document:	\	.net\Enterprise\Sites\USCBG\Depts\BioStat\Boehringer\Documentation\SAP\Final	
Author:		Version Number:	1.0

Template No.: RWI_TP_BIOS0013 Revision 1 Reference: RWI_WI_BIOS0015

Effective Date: 15Jun2018

(SD) of 18 points, and a 95% confidence interval (CI), a sample size of at least 50 patients will enable the estimation of a population mean total PASAPQ score within a margin of error (precision) of ± 5.0 points. Assuming that 10% of patients will not have evaluable data (i.e. loss to follow-up), a total number of 56 patients is required.

To test for differences in the mean total PASAPQ score in Respimat® SMI-experienced patients switching from a disposable to a re-usable Respimat® SMI product at study entry, the minimum clinically important difference for PASAPQ, which has been previously reported as 8-10 points, will be used [2]. A sample size of 56 patients will have a 90% power to detect a minimum 8-point difference in total PASAPQ score means assuming SD of differences of 18 points, using a paired t-test with a 5% two-sided significance level.

To account for potential 10% of patients with no evaluable data, a total sample size of minimum 63 patients is required. If the difference in the mean total PASAPQ score is further reduced to 6 points, the sample size will increase to 107 patients, accounting for a potential 10% patients with no evaluable data at the follow-up assessment. Different scenarios, depending on the desired power (80% or 90%) and mean difference of total PASAPQ score (6-, 8- and 10-point difference) and considering an 18-point SD of differences are presented in [Table 3](#).

Table 3 Sample size scenarios for detecting difference in total PASAPQ score means

	Scenario 1	Scenario 2	Scenario 3	Scenario 4	Scenario 5	Scenario 6
Significance level (α)	0.05	0.05	0.05	0.05	0.05	0.05
Mean difference of total PASAPQ score	6	6	8	8	10	10
SD of differences	18	18	18	18	18	18

Document: \\ .net\Enterprise\Sites\USCBG\Depts\BioStat\Boehringer\Documentation\SAP\Final

Author: Version Number: 1.0
Version Date: 100CT2019

Template No.: RWI_TP_BIOS0013 Revision 1

Reference: RWI_WI_BIOS0015

Effective Date: 15Jun2018

	Scenario 1	Scenario 2	Scenario 3	Scenario 4	Scenario 5	Scenario 6
Power (%)	80	90	80	90	80	90
Sample size, n	73	97	42	56	28	37

In this study, a total of 250 patients will be enrolled, which is adequate to meet the primary and the secondary outcomes of the study. Further, subgroup analyses will be performed only if the subgroups of interest include more than 20% of all patients.

7. ANALYSIS SETS

One analysis set will be defined for this study as outlined below.

7.1 Full Analysis Set

The Full Analysis Set (FAS) will contain all enrolled subjects who met all the eligibility criteria of this study and who have received at least one dose of their re-usable Respimat® SMI product during the study period. The FAS will be the analysis set for descriptive, primary and secondary outcome analyses.

8. GENERAL CONSIDERATIONS

8.1 Enrolled Patients

All patients who provided signed Informed Consent Form (ICF) for this study.

8.2 Eligible Patients

All patients who met all the eligibility criteria of this study.

Document:	\	.net\Enterprise\Sites\USCBG\Depts\BioStat\Boehringer\Documentation\SAP\Final	
Author:		Version Number:	1.0

Template No.: RWI_TP_BIOS0013 Revision 1 Reference: RWI_WI_BIOS0015

Effective Date: 15Jun2018

8.3 Study Discontinuation

Patients may be discontinued from the study at any time. The following events will be considered as early termination from the study:

- Adverse Event.
- Death.
- Lost to follow-up.
- Poor compliance to protocol.
- Study terminated by sponsor.
- Withdrawal by patient.
- Other.

All data collected from patients who discontinue from the study before completion will be included in all analyses.

8.4 Baseline Visit

The routine visit, at which a patient is enrolled in the study (time of ICF signature), will be treated as the baseline (study entry) visit.

8.5 End of Study Date

End of study date will be defined as the date of the earliest of the following events:

- Discontinuation (see [Section 8.3](#)).

Document: \\ .net\Enterprise\Sites\USCBG\Depts\BioStat\Boehringer\Documentation\SAP\Final

Author: Version Number: 1.0

Version Date: 100CT2019

Template No.: RWI_TP_BIOS0013 Revision 1

Reference: RWI_WI_BIOS0015

Effective Date: 15Jun2018

- End of study period/Follow-up assessment (i.e. approximately 4-6 weeks after the baseline visit).

8.6 Study Observation Period

The study observation period will start on the date of signed ICF (study enrolment date) until the end of study date (see [Section 8.5](#)). The study duration (days) will be calculated as follows:

$$\text{Study duration (days)} = [(End \text{ of study date} - date \text{ of signed ICF}) + 1]$$

8.7 Pooling of Sites

For all analyses, all data across study sites will be pooled. The “site” factor will not be considered for subgroup analyses.

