### **9.2.2 Study sites**

It is planned that approximately 250 patients (Respimat SMI-experienced and Respimat SMI-naïve) from approximately 32 sites in up to 10 European countries, potentially including (but not limited to) Belgium, Denmark, Finland, Germany, Netherlands, Norway, Romania and Sweden, will be enrolled in this study. Site selection will be performed to reflect the distribution of routine COPD care in the participating countries in order to secure a representative population of COPD patients. This may include public and private hospitals and clinics, university hospitals, specialist medical centres, and community-dwelling general practitioners and specialists. Patients may be treated by general practitioners or specialist physicians, including pneumologists.

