## **9.5 STUDY SIZE**

The primary objective of this study is to assess patient satisfaction for the re-usable Respimat SMI, measured by the total mean score of PASAPQ. Assuming a population standard deviation (SD) of 18 points, and a 95% confidence interval (CI), a sample size of at least 50 patients will enable the estimation of a population mean total PASAPQ score within a margin of error (precision) of  $\pm 5.0$  points. Assuming that 10% of patients will not have evaluable data (i.e. loss to follow-up), a total number of 56 patients is required.

To test for differences in the mean total PASAPQ score in Respimat SMI-experienced patients switching from a disposable to a re-usable Respimat SMI product at study entry, the minimum clinically important difference for PASAPQ, which has been previously reported as 8-10 points, will be used ([Hodder and Price 2009](#)). A sample size of 56 patients will have a 90% power to detect a minimum 8-point difference in total PASAPQ score means assuming SD of differences of 18 points, using a paired t-test with a 5% two-sided significance level. To account for potential 10% of patients with no evaluable data, a total sample size of minimum 63 patients is required. If the difference in the mean total PASAPQ score is further reduced to 6 points, the sample size will increase to 107 patients, accounting for a potential 10% patients with no evaluable data at follow-up assessment. Different scenarios, depending on the desired power (80% or 90%) and mean difference of total PASAPQ score (6-, 8- and 10-point difference) and considering an 18-point SD of differences are presented in Table 5.

Table 5: Sample size scenarios for detecting difference in total PASAPQ score means

	Scenario 1	Scenario 2	Scenario 3	Scenario 4	Scenario 5	Scenario 6
Significance level ( $\alpha$ )	0.05	0.05	0.05	0.05	0.05	0.05
Mean difference of total PASAPQ score	6	6	8	8	10	10
SD of differences	18	18	18	18	18	18
Power (%)	80	90	80	90	80	90
Sample size, n	73	97	42	56	28	37

In this study, a total of 250 patients will be enrolled, which is adequate to meet the primary and the secondary outcomes of the study. Further, subgroup analyses will be performed only if the subgroups of interest include more than 20% of all patients.

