## **9.9 LIMITATIONS OF THE RESEARCH METHODS**

The intention of this non-interventional study (NIS) is to collect data on patient satisfaction and preference for the re-usable Respimat SMI in a real life setting in patients with COPD. However, heterogeneities in health-seeking behaviour, treatment and reporting practices between countries and sites within countries may introduce selection and information bias. Moreover, due to the real-world nature of the study and due to variabilities in efficiency and completeness of records, missing data are likely to be present and this may vary by country and/or site.

The sites selected will be a convenience sample and may not be representative of the geographic distribution or the clinic/hospital type or size in each of the participating countries. The enrolment will be competitive, although there may be capping at the country level to ensure that all countries are represented.

At the patient level, consecutive enrolment will be employed to minimise selection bias. Potential selection bias arising from the lack of complete enrolment of potentially eligible patients will be reduced by maintaining screening logs at sites. The eligibility criteria are largely non-restrictive, which will permit the enrolment of a broad COPD-patient population. The choice of treatment is at the discretion of the investigator, reflective of real-world clinical practice.

Information bias will be minimised by using standard eCRF, questionnaires and physicians' training on the study protocol. The patients' interpretation and understanding of the questionnaires and different educational backgrounds may also influence the results. Further, while the PASAPQ questionnaire has been validated ([Kozma et al. 2005](#)), the additional questions on the ease of handling of the re-usable Respimat SMI is a self-designed BI questionnaire.

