9. STATISTICAL CONSIDERATIONS

9.1 Statistical Tests and Confidence Intervals

Unless otherwise specified in the description of the analyses, all statistical tests will be two-sided and performed considering a significance level of 0.05. All statistical tests are exploratory due to the nature of the study, therefore no adjustment for multiplicity is considered in this SAP.

Whenever applicable, two-sided 95% CIs for proportions calculated using the exact Binomial (Clopper-Pearson) method [3] and 95% CIs of a normal distribution for means will be provided.

The normality assumption of the distributions of continuous variables will be tested using the Kolmogorov-Smirnov test (if $n \geq 50$) or Shapiro Wilk test (if $n < 50$). In addition, the visualisation of data distribution (skewness and kurtosis) may be performed using histograms/box-plot. Non-parametric tests will be used whenever the normality assumption is not accepted.

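### The 95% CI for the primary mean PASAPQ score treats patients from about 32 sites as independent, so it will be too narrow if scores correlate positively within site

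*SAP*

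**What the plan says.** The primary analysis (Protocol 9.7.1.1, SAP 20.1.1) is descriptive: the mean total PASAPQ score at follow-up with its 95% CI, overall and by cohort. No test is attached to it.

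On sites, SAP 8.7 states: "For all analyses, all data across study sites will be pooled". It then excludes site as a factor in subgroup analyses. On method, SAP 9.1 states that "95% CIs of a normal distribution for means will be provided" and specifies Clopper-Pearson limits for proportions. Both methods assume independent patients. Neither document mentions a cluster-robust variance, a random effect for site or country, an ICC, a design effect or a sensitivity analysis for clustering.

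On recruitment, Protocol 9.2.2 plans "approximately 32 sites in up to 10 European countries". Under Protocol 9.1 enrolment is competitive, and a site or country need not contribute to both cohorts. Protocol 9.9 warns that "heterogeneities in health-seeking behaviour, treatment and reporting practices between countries and sites within countries may introduce selection and information bias".

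**The concern.** A normal-theory CI for a mean has its nominal coverage when the observations are independent. Here patients are grouped within sites, and several features make it plausible that patients of one site resemble each other. They share a care setting, which ranges from general practice to university hospital. They share a country, and with it the questionnaire language and the available pack size. The protocol itself expects reporting practices to vary between sites and countries, and the outcome is a self-reported score. Competitive enrolment will probably make site sizes unequal, which enlarges the effect of any such correlation.

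What is at stake is the accuracy of the reported interval. In a descriptive study the CI around the primary mean is the main inferential result. An interval labelled 95% that covers the true mean 88% of the time overstates what was learned.

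**Working it through.** **Inputs from the documents**
- SD 18 points, 95% confidence, half-width 5.0 points, 10% not evaluable (Protocol 9.5, SAP 6).
- 250 patients enrolled (same sections); 250 × 0.9 = 225 evaluable.
- About 32 sites (Protocol 9.2.2); 225 / 32 = 7.03 evaluable patients per site.

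**Assumed, because the documents do not give them**
- ICC of 0.01, 0.05 or 0.10.
- Coefficient of variation (CV) of site size of 0 (equal sites) or 0.8.

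**Step 1: the plan's own figure.** The plan says: "Assuming a population standard deviation (SD) of 18 points, and a 95% confidence interval (CI), a sample size of at least 50 patients" gives the mean "within a margin of error (precision) of ± 5.0 points". Check: n = (1.96 × 18 / 5)² = 49.8, rounded up to 50; 50 / 0.9 = 55.6, rounded up to 56. Both figures reproduce exactly with a design effect of 1, that is, with independent patients.

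**Step 2: half-width under independence.** 1.96 × 18 / √225 = ±2.35 points. (With all 250 patients it would be ±2.23.)

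**Step 3: allow for clustering.**
- Design effect: DE = 1 + [m(1 + CV²) − 1] × ICC, with m = 7.03.
- Correct half-width: 2.35 × √DE.
- True coverage of the planned interval: 2Φ(1.96 / √DE) − 1.
- The bracket equals 6.03 for CV 0, and 7.03 × 1.64 − 1 = 10.53 for CV 0.8.

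| Assumed ICC | Assumed CV | DE | Correct half-width | Coverage of nominal 95% CI |
|---|---|---|---|---|
| 0.01 | 0 | 1.06 | ±2.42 | 94.3% |
| 0.05 | 0 | 1.30 | ±2.68 | 91.4% |
| 0.10 | 0 | 1.60 | ±2.98 | 87.8% |
| 0.01 | 0.8 | 1.11 | ±2.47 | 93.8% |
| 0.05 | 0.8 | 1.53 | ±2.91 | 88.7% |
| 0.10 | 0.8 | 2.05 | ±3.37 | 82.9% |

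**Step 4: is the ±5.0 target at risk?** It would be lost only at DE above (5 / 2.352)² = 4.52. That needs an ICC above (4.52 − 1) / 6.03 = 0.58 with equal sites, or above 3.52 / 10.53 = 0.33 with CV 0.8. Both lie far outside the range considered.

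**Step 5: other intervals.**
- *Cohort means.* The design effect depends on patients per site within the cohort. If half the evaluable sample were spread evenly over 32 sites, m = 112.5 / 32 = 3.5. At ICC 0.05, DE is then 1 + 2.52 × 0.05 = 1.13 and coverage 93.5%. If a cohort is concentrated in fewer sites, which Protocol 9.1 permits, m and the design effect rise.
- *Paired change in switchers.* A site effect common to both visits cancels in the difference. Only site differences in the change itself remain.
- *Preference proportion.* It is exposed in principle, but it depends on how switchers are spread over sites and is not quantified here.

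Country is a further possible level of clustering, also not quantified.

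**The case against.** The strongest reply is that nothing in the documents shows that PASAPQ scores correlate within sites. Protocol 9.9 speaks of selection and information bias, not of correlated scores. The questionnaire is self-administered and often completed away from the clinic, and language is a country feature rather than a site feature. At ICC 0.01 with equal sites the half-width moves by 0.07 points. At ICC 0.05 it moves by 0.33 points on a 0–100 scale, against a cited minimum important difference of 8–10 points. The primary analysis has no decision threshold and all tests are labelled exploratory, so no planned conclusion would change. Clustered standard errors also become unreliable with few clusters.

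Much of this stands. It is why the point is conditional and the ICC is shown as a range, and why small cohorts need caution. It does not remove the point. The exploratory label concerns tests, whereas the primary result is an interval. A large sample does not help either: with the number of sites fixed, more patients per site raise the design effect.

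Four stronger readings are tempting, and the documents do not support them:
- *The CI is certainly too narrow.* This needs an ICC, and none is given.
- *The study is too small.* The plan requires 56 patients for the primary objective ("Assuming that 10% of patients will not have evaluable data (i.e. loss to follow-up), a total number of 56 patients is required") and enrols 250, about 4.5 times as many. Step 4 shows that the target precision holds.
- *The SAP instructs the analyst to ignore site in variance estimation.* SAP 8.7 excludes site only from subgroup analyses. Independence follows from the methods in SAP 9.1 and 20.1.1 and from the absence of any clustering method, so there is no sentence on variance to delete.
- *Every interval is affected alike.* Step 5 shows otherwise.

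**Conclusion.** The concern holds in conditional form. The planned 95% CI for the primary mean rests on independence between patients of the same site. It will be too narrow if scores correlate positively within site, which is plausible from the protocol's own description but not demonstrated.

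With 225 evaluable patients in 32 sites, the loss is trivial at an assumed ICC of 0.01 and material at 0.05 to 0.10. At those values coverage is about 91% to 88% with equal sites, and about 89% to 83% with an assumed CV of 0.8. The point estimate and the claim that the study size is adequate are not challenged. This is an inexpensive improvement to how precision is reported, not a flaw that invalidates the study.

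**What to change.** 1. Keep the pooled mean as the primary estimate. In SAP 9.1 and 20.1.1, add a site-clustered 95% CI for it, for example from PROC SURVEYMEANS with site as the cluster or from an intercept-only model with a random site effect. Base the degrees of freedom on the number of sites (31 with 32 sites).
2. Report the observed ICC and the distribution of site sizes, so that readers can see how much clustering there was.
3. Give site-clustered intervals for the cohort means and the preference proportion beside the planned ones, where enough sites contribute. State in advance the minimum number of sites for doing so. Keep the Clopper-Pearson intervals.
4. For the paired change, a clustered interval is optional, since only site differences in change affect it.

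SAP 8.7 can stay as it is; a cross-reference to the new text is enough.

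Cost: a few lines of code in SAS 9.4, which the SAP already names, and no new data. The interval becomes somewhat wider if scores do correlate within site and barely changes if the ICC is near zero. Clustered standard errors are less reliable where a cohort comes from few sites, which is why item 3 has a condition.
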